NOACs, or also known as direct oral anticoagulants (DOACs), are a relatively new generation of anticoagulants approved by the US FDA; dabigatran, rivaroxaban, apixaban, and edoxaban were approved in October 2010, July 2011, December 2012, and January 2015, respectively, for treatment indication of risk reduction of stroke and embolism in nonvalvular atrial fibrillation (NVAF) [6]. These NOACs have also been approved for prophylaxis and treatment of DVT and PE, which comprise VTE [7, 8]. Compared with VKAs, NOACs have fewer drug interactions, food interactions, and adverse effects and therefore, do not require frequent laboratory monitoring or dosage adjustments [4, 9]. Among NOACs, apixaban and rivaroxaban were approved as a single-drug approach for the treatment of VTE and do not require initial parenteral treatment with low molecular weight heparin (LMWH) or unfractionated heparin (UFH) [10, 11]. In actual real-world clinical practice, the two aforementioned NOACs are the most widely used and preferred treatments for VTE and preventing its recurrence [12-14]. Although NOACs demonstrated better safety profile than VKAs, concerns regarding their risk of adverse bleeding events remain due to their mechanism of action [15].

With both conventional and new anticoagulant therapies being used in real-world clinical practice, it is necessary to identify the utilization characteristics of individual anticoagulant treatments through the analysis of nationwide claims database. It is important to examine the treatment pattern and assess whether Korean patients are being treated appropriately based on the current treatment guidelines.

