Cancer surgeries	Specified in 'cancer-related surgery' of section 8.3.2
Benign surgeries	R4123-R4129, R4421, R4430, R3975
Cancer-related event (active cancer)	C00-C97 (excluding non-melanoma skin cancer, C44) with V code (V011, V027, V193, V194)
Kidney function change	
Chronic kidney disease	N18, N19
Acute kidney injury	N17
Liver function change	
Liver disease	B15-B19, K70-K77
Abnormal liver function	R94.5, R74.0

- **Phase II of the study**

- Major bleeding will be defined using primary or secondary diagnosis codes according to the ICD-10 diagnostic codes shown in below table and classified by site (intracranial, gastrointestinal [GI], all others).

Major bleeding	ICD-10 diagnosis code	Diagnostic definition
Intracranial hemorrhage	I60, I61, I62, I690, I691, I692, S064, S065, S066, S068	Diagnosis code + admission code + brain CT or MRI code

		* Brain CT or MRI: CT: HA441, HA451, HA461, HA471, HA851 MRI: HE101, HE102, HE135, HE201, HE202, HE235, HE301, HE302, HE401, HE402, HE501, HE502, HE535
GI bleeding	I850, I983, K2211, K226, K228, K250, K252, K254, K256, K260, K262, K264, K266, K270, K272, K274, K276, K280, K282, K284, K286, K290, K3181, K5521, K625, K920, K921, K922	Diagnosis code + admission code
Other bleeding	D62, H448, H3572, H356, H313, H210, H113, H052, H470, H431, I312, N020-N029, N421, N831, N857, N920, N923, N930, N938, N939, M250, R233, R040, R041, R042, R048, R049, T792, T810, N950, R310, R311, R318, R58, T455, Y442, D683	Diagnosis code + admission code

- The earliest date of diagnosis of the major bleeding event after the index date will be defined as the outcome occurrence date.
- Patients will be followed up from the index date to the occurrence of an outcome, treatment discontinuation (30-day grace period), switch to another anticoagulants, in-hospital death, or end of the study period (31 Dec 2019) whichever comes first.

Potential Confounder(s)

- Sociodemographic characteristics such as age, sex, and index year will be assessed at the index date.
- CCI [2] and HAS-BLED [3] scores will be measured within the 6-month period prior to the index date.

List of CCI	Score	ICD-10 codes
Cerebrovascular disease	1	G45, G46, H34, I60-I69
Congestive heart failure	1	I09.9, I11.0, I13.0, I13.2, I25.5, I42.0, I42.5-I42.9, I43, I50, P29.0
Chronic pulmonary disease	1	I27.8, I27.9, J40-J47, J60-J67, J68.4, J70.1, J70.3

Dementia	1	F00–F03, F05.1, G30, G31.1

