9. STUDY SIZE

Phase I of the study (descriptive)

Not applicable as there are no specified *a priori* hypotheses

Phase II of the study (comparative)

- The estimated number of incident patients with VTE and no history of active cancer from the 2018 HIRA-National Patient Sample (HIRA-NPS) database is 1,465, where the HIRA-NPS database is a 3% random sample of the entire Korean population of 50 million. Based on this estimation, the projected number of patients with VTE from the entire Korean population (HIRA database) of 2018 is 48,828 (1,465 * 33.33).
 - Excluding period for patients with previous OAC treatment, VTE history or a history of active cancer was set to prior 3 months because HIRA NPS database used in sample size estimation was constituted of one-year data only.

1) Apixaban vs. warfarin

- Among the above-mentioned number of incident patients with VTE and no history of active cancer, those who newly initiated apixaban or warfarin was estimated to be 211 patients (14.4%; 211/1,465), where patients had no prescription for OACs and no history of VTE within the 3-month period prior to VTE diagnosis. From these 211 patients, there were 83 (39.3%) apixaban users and 128 (60.7%) warfarin users (based on 2018 HIRA-NPS data). Hence, the projected number of patients with VTE who newly initiated OACs to be present in the HIRA database in a single year is 7,032 patients (apixaban 2,766; warfarin 4,266). As this study aims to utilize data from 2013 to 2019 (7 years), the final projected number of patients with VTE who newly initiated apixaban or warfarin from the HIRA database is 49,224 patients (apixaban 19,362; warfarin 29,862).
- Considering a 95% for a two-sided CI level (α -error=0.05) and 80% power, the sample size for the comparative safety study for major bleeding events was calculated based on the following components:
 - HR for major bleeding events from previous literature: 0.31-0.75
 - Overall probability of major bleeding events from previous literature: 1.19%
 - Proportion of apixaban users among patients with VTE from the 2018 HIRA-NPS database: 39.3% (83 apixaban users; 128 warfarin users).

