- In the NOAC-based group, all analyses will be repeated stratified by each individual NOAC class (e.g, apixaban, dabigatran, rivaroxaban, edoxaban) to

PFIZER CONFIDENTIAL

identify the difference in baseline characteristics and treatment patterns between each NOAC class.

- To identify potential reasons for treatment change, clinical events preceding the first treatment change (major bleeding, thromboembolism diagnosis, complications of VTE, major surgery, active cancer, a new diagnosis of CKD or AKI, a new diagnosis of liver disease or abnormal liver function) will be measured within 30 days prior to the first date of treatment change. Patients can contribute with multiple events.
- All analyses of treatment patterns will be presented stratified according to the index anticoagulant treatment, and not overall or per drug class.

Phase II of the study (comparative)

Propensity score analysis

- To balance and adjust for any potential differences in baseline sociodemographic and clinical characteristics between treatment groups, propensity score (PS) methods will be implemented.
 - A logistic regression model will be used to estimate the predicted probability (propensity) of initiating each NOAC compared with warfarin given baseline covariates mentioned above. By using the estimated PS, we will apply the PS based on the inverse probability of treatment weights (IPTW), where the treatment group of interest will be given a weight of 1/PS, and the comparator group will be given a weight of 1/(1-PS) [4, 5]. The most extreme 1% of PS values (IPTW with trimming) will be excluded to improve comparability between exposure groups.

Main Analysis

- Sociodemographic and clinical characteristics will be summarized with means (STD) or median (IQR) for continuous variables and with count (proportions) for categorical variables for the two treatment comparisons of: apixaban vs warfarin, rivaroxaban vs warfarin, edoxaban vs warfarin and dabigatran vs warfarin (and NOAC vs NOAC, if scientifically feasible).
 - Differences in baseline covariates between users of different OACs will be assessed using the SD where the absolute SD <0.1 will be considered as well balanced.
- The incidence rate of major bleeding overall and by site will be presented as the total number of events per 1,000 person-years, with its 95% CIs estimated using the Poisson distribution.

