- The risk of major bleeding according to the treatment of interest will be investigated in time-to-event analyses using standard Kaplan-Meier methods.

- Cox proportional hazards model will be used to compare the safety outcome between users of different OACs, weighted on the estimated PS according to the IPTW approach.
 - Proportionality assumption will be tested by use of Schoenfeld residuals.

Subgroup Analysis

- The potential heterogeneity of treatment effects in selected subgroups of patients with VTE will be examined for the major bleeding as follows:
 - Aged <65 years vs. aged \geq 65 years
 - Females vs. males
 - Setting of VTE diagnosis (inpatient vs. outpatient)
 - Type of VTE (DVT without PE [ICD-10: I80.2, I80.3] vs. PE with or without DVT [I26.0, I26.9])
 - Major orthopedic surgery-provoked VTE
 - Major orthopedic surgery-provoked VTE is defined as an event preceded by knee arthroplasty, hip arthroplasty, or hip fracture surgery (National Procedure Codes: N0305, N0601, N0611, N0641, N0711, N2070, N0715, N2710, N0731, N0981, N0991, N1711, N3710, N1721, N3720, N1715, N4710, N1725, N4720, N2072, N2077, N2712, N2717, N3712, N3717, N3722, N3727, N4712, N4717, N4722 or N4727) within 3 months period prior to index date
 - With vs. without CKD stage 3 or 4 (N18.3, N18.4)
- P-for-interaction value <0.05 will be used to denote a significant difference between the two groups.

Sensitivity Analysis

- Vary the definition of treatment interruption/discontinuation to 15 and 60 days (allowing for varying non-adherence) to assess the effect this had on study outcomes.
- Four other approaches involving PS will be applied to determine the robustness of our study findings. First, we will vary the extreme value of PS in trimming process (most extreme 5%, and 10% will be excluded). Second, we will include the estimated PS, in addition to other covariates, into our multivariable Cox proportional hazards regression model. Third, we will stratify on the estimated PS in deciles. Last, we will apply another weighting approach, standardized mortality ratio weights, with the weights given as follows: 1 for the treatment group of interest and PS/(1 – PS) for the comparator group.[4]

- Exclude patients with a history of bleeding during the 6-month pre-index-date period in Phase II comparative analysis to evaluate the robustness of findings with respect to changes in underlying risk of patients

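### Setting of VTE diagnosis and recent major orthopaedic surgery serve in Phase II only as subgroup variables and are missing from the propensity model, so the primary hazard ratios are open to avoidable confounding of unknown size and direction

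*SAP*

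**What the plan says.** **Propensity model.** SAP section 10 (Protocol 9.7 agrees) models the probability of "initiating each NOAC compared with warfarin given baseline covariates mentioned above". The covariates meant are the potential confounders in SAP 8.4 and Protocol 9.3: age, sex, index year, CCI, HAS-BLED, DVT/PE presentation, named comorbidities (fracture and trauma among them), prior medications and the number of outpatient visits. Setting of diagnosis, orthopaedic procedures and prior admission are not listed.

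**Balance tables.** SAP Tables 13-16 have no row for setting or orthopaedic surgery. They also lack DVT/PE presentation, which is a listed confounder.

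**Where the two variables are used.** The Phase II subgroup list includes "Setting of VTE diagnosis (inpatient vs. outpatient" and VTE provoked by major orthopaedic surgery, defined by procedure codes within 3 months before index. Both appear in Table 19. In Phase I, orthopaedic-provoked VTE is also a descriptive row in Table 1, and the same procedure codes define one of the events preceding a treatment change.

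**Outcome.** For gastrointestinal and other bleeding SAP 8.4 requires "Diagnosis code + admission code"; intracranial bleeding needs brain imaging as well. A primary or secondary diagnosis is enough. The bleeding diagnosis must fall after the index date, but the text does not say that the admission must.

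**Eligibility.** VTE diagnosed in either an inpatient or an outpatient setting qualifies, and anticoagulation may start up to 30 days after diagnosis.

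**The concern.** A baseline variable needs adjustment if it is related to both drug choice and the outcome. Setting is a plausible candidate on both counts.

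- **Outcome.** An admission is part of the definition at every site. As written, a patient in hospital when treatment starts might satisfy that part with the current stay, whereas an outpatient starter has to be admitted first. Setting could then affect ascertainment as well as reflect severity.
- **Drug choice.** Protocol section 7 states that "apixaban and rivaroxaban were approved as a single-drug approach for the treatment of VTE and do not require initial parenteral treatment". That ties the choice of these two drugs to acute management. The step from there to outpatient starts is an inference, and the passage says nothing comparable about edoxaban or dabigatran.

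Recent orthopaedic surgery may likewise relate to drug choice and to bleeding. The other-bleeding row, which needs no imaging, includes D62, M250, T792 and T810.

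The primary objective of Phase II is to compare major bleeding between anticoagulants, and it rests on the weighted hazard ratios in Table 17.

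**Working it through.** **Step 1. Reproduce the plan's sample size.** The inputs come from SAP section 9: two-sided alpha 0.05 ("Considering a 95% for a two-sided CI level"), 80% power and, for apixaban, "HR for major bleeding events from previous literature: 0.31-0.75", an overall event probability of 1.19% and a 39.3% share on apixaban.

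Schoenfeld events at HR 0.75: D = (1.96 + 0.842)² / [0.393 × 0.607 × (ln 0.75)²] ≈ 398. Then N = 398 / 0.0119 ≈ 33,446, against 33,340 stated. The same formula reproduces all eight stated sizes within 3%. The sample-size arithmetic is not in dispute.

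**Step 2. Events on the plan's own inputs** (projected cohort × event probability):

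- Apixaban: 49,224 × 0.0119 ≈ 586
- Rivaroxaban: 89,124 × 0.081 ≈ 7,219
- Edoxaban: 42,924 × 0.085 ≈ 3,649
- Dabigatran: 36,162 × 0.014 ≈ 506

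**Step 3. Bias factor for one omitted binary covariate.** B = [pN(R − 1) + 1] / [pW(R − 1) + 1]. Here pN and pW are its prevalences on NOAC and warfarin, and R is its bleeding rate ratio. B is the apparent HR when the true HR is 1. The documents give none of pN, pW or R, so every row is an assumption.

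| Covariate | pW | pN | R | B |
|---|---|---|---|---|
| Inpatient diagnosis | 50% | 45% | 1.5 | 1.225/1.25 = 0.98 |
| Inpatient diagnosis | 60% | 50% | 1.5 | 1.25/1.30 = 0.96 |
| Inpatient diagnosis | 70% | 60% | 2 | 1.6/1.7 = 0.94 |
| Inpatient diagnosis | 60% | 40% | 1.5 | 1.2/1.3 = 0.92 |
| Inpatient diagnosis | 60% | 40% | 2 | 1.4/1.6 = 0.88 |
| Inpatient diagnosis | 80% | 60% | 3 | 2.2/2.6 = 0.85 |
| Inpatient diagnosis | 70% | 40% | 2 | 1.4/1.7 = 0.82 |
| Inpatient diagnosis | 90% | 60% | 3 | 2.2/2.8 = 0.79 |
| Orthopaedic surgery | 5% | 10% | 2 | 1.10/1.05 = 1.05 |
| Orthopaedic surgery | 5% | 15% | 2 | 1.15/1.05 = 1.10 |

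Reversing the assumed prevalences reverses the direction. R is applied to all on-treatment time. If the excess is confined to the days around admission, the effective R is smaller. Listed covariates that correlate with setting would absorb part of B.

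**Step 4. Does a large cohort protect?** With true HR 1 and share a on the NOAC, the test statistic is shifted by ln(B) × √[D × a × (1 − a)]. For rivaroxaban at B = 0.962 the shift is −0.0387 × √(7,219 × 0.691 × 0.309) ≈ −1.52, which gives p < 0.05 in about 33% of studies. Variance inflation from weighting is ignored, so these figures are somewhat high.

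| B | Apixaban | Rivaroxaban | Edoxaban | Dabigatran |
|---|---|---|---|---|
| 0.96 | 7% | 33% | 19% | 6% |
| 0.92 | 16% | 88% | 61% | 10% |

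Size gives no protection: the more events a comparison has, the more readily a small bias reaches significance.

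**The case against.** The case for leaving the plan alone has real content.

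- **Table 19 is informative.** It reports patients and events by drug within each setting, with weighted HRs and an interaction P. A reader might infer that an imbalance in setting would go unseen; that is not so, because the crude split will be visible and stratum HRs are a partial check. What Table 19 does not do is adjust the headline HR or show balance after weighting. It also has no non-orthopaedic comparison row.
- **Surgery is not confined to subgroups across the whole study.** It is also a Phase I Table 1 row. The omission is from Phase II adjustment.
- **Proxies exist.** Fracture, trauma, DVT/PE presentation, CCI, HAS-BLED and outpatient visits may carry some of the information. None records setting at diagnosis or a surgical procedure.
- **Other safeguards.** The alternative propensity analyses change trimming, stratification or weights, not the covariates. The covariate-adjusted Cox model refers to other covariates without naming them. The E-value in Protocol 9.9 names apixaban only and does not appear in the SAP, and a recorded variable is better adjusted for than bounded.
- **Very high inpatient shares on warfarin need support.** Exclusion 5 removes patients given two anticoagulants on the index date, so those starting heparin and warfarin on the same day are out. This weakens the 80-90% scenarios.
- **The mechanism rests on a reading.** The SAP does not say whether an admission code from an ongoing index stay qualifies.

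**Conclusion.** The omission is real and worth correcting as a low-cost improvement. Two variables already defined for Phase II subgroups are absent from the propensity model and from its balance tables, while the outcome definition depends on admission. The primary hazard ratios are open to avoidable confounding; the documents do not show that they are biased.

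Two stronger conclusions are tempting and are not supported.

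- **That each NOAC will look safer than it is.** No split of either variable by drug is given, the treatment-choice passage covers only apixaban and rivaroxaban, and the assumed surgery scenarios push upwards while the setting scenarios push downwards.
- **That the bias matches the effects the study is sized for.** Of the scenarios above, only 90% against 60% with R = 3 (B = 0.79) comes close to the apixaban planning HR of 0.75, and the conservative planning HRs for the other drugs are 1.19, 0.81 and 0.69.

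Under the assumed range, a true HR of 0.75 would be estimated between 0.75 × 0.786 ≈ 0.59 and 0.75 × 1.095 ≈ 0.82. That range depends wholly on the assumed prevalences and rate ratios.

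**What to change.** 1. Add setting of VTE diagnosis (inpatient or outpatient) and major orthopaedic surgery within 3 months before index to the potential confounders in SAP 8.4 and Protocol 9.3, and to each propensity model.
2. Add both as rows in Tables 13-16, together with the missing DVT/PE presentation row, so that balance is checked before and after weighting.
3. Add one sensitivity analysis that counts only bleeds from admissions starting after the index date. Setting of diagnosis is not the same as being in hospital at index, which can fall up to 30 days later, so step 1 alone addresses the ascertainment question only in part. This should remain a sensitivity analysis, because it discards true in-hospital bleeds.

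**Cost:** wording in two documents, two model terms from variables already defined, and one extra analysis. The sample size does not change. The downside is slightly more variable weights if setting strongly predicts drug choice.

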- In the NOAC-based group, all analyses will be repeated stratified by each individual NOAC class (e.g, apixaban, dabigatran, rivaroxaban, edoxaban) to identify the difference in baseline characteristics and treatment patterns between each NOAC class.
- To identify potential reasons for treatment change, clinical events preceding the first treatment change (major bleeding, thromboembolism diagnosis, complications of VTE, major surgery, active cancer, a new diagnosis of CKD or AKI, a new diagnosis

of liver disease or abnormal liver function) will be measured within 30 days prior to the first date of treatment change. Patients can contribute with multiple events.

- All analyses of treatment patterns will be presented stratified according to the index anticoagulant treatment, and not overall or per drug class.

Phase II of the study (comparative)

Propensity score analysis

- To balance and adjust for any potential differences in baseline sociodemographic and clinical characteristics between treatment groups, propensity score (PS) methods will be implemented.
 - A logistic regression model will be used to estimate the predicted probability (propensity) of initiating each NOAC compared with warfarin given baseline covariates mentioned above. By using the estimated PS, we will apply the PS based on the inverse probability of treatment weights (IPTW), where the treatment group of interest will be given a weight of 1/PS, and the comparator group will be given a weight of 1/(1-PS) [25, 26]. The most extreme 1% of PS values (IPTW with trimming) will be excluded to improve comparability between exposure groups.

Main Analysis

- Sociodemographic and clinical characteristics will be summarized with means (STD) or median (IQR) for continuous variables and with count (proportions) for categorical variables for the two treatment comparisons of: apixaban vs warfarin, rivaroxaban vs warfarin, edoxaban vs. warfarin and dabigatran vs. warfarin (and NOAC vs. NOAC, if scientifically feasible).
 - Differences in baseline covariates between users of different OACs will be assessed using the SD where the absolute SD <0.1 will be considered as well balanced.
- The incidence rate of major bleeding overall and by site will be presented as the total number of events per 1,000 person-years, with its 95% CIs estimated using the Poisson distribution.

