10. STATISTICAL ANALYSIS

All statistical analyses will be performed using SAS Enterprise Guide 7.1 (SAS Institute Inc., Cary, NC, USA), provided by HIRA through a virtual access machine.

Phase I of the study (descriptive)

Main Analysis

- Descriptive analysis will be conducted separately in two cohorts of non-cancer VTE and cancer VTE patients according to co-presence of active cancer.
- Sociodemographic and clinical characteristics will be summarized with means (standard deviations [STD]) or median (interquartile range [IQR]) for continuous variables and with count (proportions) for categorical variables for the three treatment groups of interest: PAC only (UFH, LMWH, UFH+LMWH), warfarin-based (warfarin, PAC/warfarin) group, NOAC-based (NOAC, PAC/NOAC) group. NOAC-based (NOAC, only group, PAC/NOAC) group. Analysis of variance, and chi-square test will be conducted for continuous variables, and categorical variables, respectively.
 - In order to distinguish between PAC bridging therapy and PAC treatment, we will apply a time restriction of 2 weeks to PAC bridging therapy.
- Temporal trend in anticoagulation therapy for VTE will be presented between 1 Mar 2013 and 30 Jun 2019. Proportions of the index OACs will be estimated according to calendar year and quarter.
- The number and percentage of patients who discontinue treatment completely, experience treatment interruption and treatment switch during their follow-up will be described by the index anticoagulant treatment received. Results will be limited to the first of each of these events for each patient. For patients experiencing a treatment switch, the new treatment will be described at the time of their first switcher per individual drug.
- The duration of the index treatment by the index anticoagulant treatment received will also be summarized in terms of days using descriptive statistics (mean [STD], median [IQR]).
- The Kaplan-Meier method will be applied to derive the empirical distribution of time to each of the treatment endpoints of interest (e.g., treatment discontinuation or switch); these analyses will be performed per index anticoagulant treatment received and no comparisons will be made. Log-rank test will be conducted at the 3-, and 6 months after treatment initiation to assess statistical significance between the survival curves. Persistent rate will also be calculated at the same time point.

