Note: ACE, angiotensin-converting enzyme; aSD, absolute standardized difference; CCI, Charlson comorbidity index; COPD, chronic obstructive pulmonary disease; IQR, interquartile range; NSAIDs, nonsteroidal anti-inflammatory drugs; PAC, parenteral anticoagulants; SSRI, selective serotonin reuptake inhibitors; std, standard deviation

Table 16. Pre- and post-weighted baseline characteristics of patients with venous thromboembolism who newly initiated dabigatran and warfarin.

Characteristics	Pre-weighted			Post-weighted		
	Dabigatran N= (%)	Warfarin- based therapy N= (%)	aSD	Dabigatran N= (%)	Warfarin- based therapy N= (%)	aSD
Follow-up (days; median, IQR)						
Age (years; mean±std)						
Age group (years; n, %)						
18-40						
40-65						
≥65						
Sex (n, %)						
Male						
Female						
Health insurance type (n, %)						
National health insurance						
Medical aid						
Index year (n, %)						
2012						
2013						
2014						
2015						
2016						
2017						
2018						
2019						
CCI score (mean±std)						
HAS-BLED score (mean±std)						
Comorbidities (n, %)						
Antiphospholipid syndrome						
Asthma						
History of cancer						
COPD						
Chronic kidney disease						
Chronic liver disease						
Diabetes mellitus						

Fracture
Heart failure
Hyperlipidemia
Hypertension
Ischemic heart disease
Myocardial infarction
Stroke
Trauma
Previous use of
medications (n, %)
Corticosteroids
NSAIDs
ACE inhibitors
Angiotensin II
receptor blockers
Aspirin
β-blockers
Calcium-channel
blockers
SSRI
Proton pump
inhibitors
Diuretics
Thiazides
Vasodilators
Estrogens
Cyclooxygenase-2
inhibitors
Outpatient visits
(mean±std)

Note: ACE, angiotensin-converting enzyme; aSD, absolute standardized difference; CCI, Charlson comorbidity index; COPD, chronic obstructive pulmonary disease; IQR, interquartile range; NSAIDs, nonsteroidal anti-inflammatory drugs; PAC, parenteral anticoagulants; SSRI, selective serotonin reuptake inhibitors; std, standard deviation

Table 17. Risk of major bleeding events in patients with venous thromboembolism who newly initiated oral anticoagulants associated with NOAC use versus warfarin

	No of Patients	No of Events	Person-years	Incidence rate* (95% CI)	Crude HR (95% CI)	IPT-Weighted HR (95% CI)
Warfarin-based						Reference (1.00)
Apixaban						
Rivaroxaban						
Edoxaban						
Dabigatran						

Note: CI, confidence interval; HR, hazard ratio; IPT, inverse probability of treatment.

*Events per 1000 person years.

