13. LIST OF FIGURES

Figure 1. Kaplan-Meier plot showing time to anticoagulant therapy interruption in patients with venous thromboembolism according to presence of active cancer.	65
Figure 2. Kaplan-Meier plot showing time to anticoagulant therapy switching in patients with venous thromboembolism according to presence of active cancer.	66
Figure 3. Kaplan-Meier plot showing time to anticoagulant therapy discontinuation in patients with venous thromboembolism according to presence of active cancer.	67
Figure 4. Trends in newly prescribed anticoagulants in patients with venous thromboembolism between Mar 2013 and Jun 2019.....	68
Figure 5. Cumulative incidence curves for the risk of major bleeding events associated with NOAC use versus warfarin	69
Figure 6. Number of weighted events, incidence rate, and hazard ratio of major bleeding events associated with NOAC use versus warfarin.	70

[figure not shown]

Figure 1. Kaplan-Meier plot showing time to anticoagulant therapy interruption in patients with venous thromboembolism according to presence of active cancer.

[figure not shown]

Figure 2. Kaplan-Meier plot showing time to anticoagulant therapy switching in patients with venous thromboembolism according to presence of active cancer.

[figure not shown]

Figure 3. Kaplan-Meier plot showing time to anticoagulant therapy discontinuation in patients with venous thromboembolism according to presence of active cancer.

[figure not shown]

Figure 4. Trends in newly prescribed anticoagulants in patients with venous thromboembolism between Mar 2013 and Jun 2019.

[figure not shown]

Figure 5. Cumulative incidence curves for the risk of major bleeding events associated with NOAC use versus warfarin

PFIZER CONFIDENTIAL

[figure not shown]

Figure 6. Number of weighted events, incidence rate, and hazard ratio of major bleeding events associated with NOAC use versus warfarin.

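### The Phase II Cox model uses unstabilised 1/PS weights and names no variance estimator; if the model-based variance is kept, the 95% CIs are too narrow

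*SAP*

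**What the plan says.** Phase II compares major bleeding between each of four NOACs and warfarin. The propensity score (PS) part of SAP section 10 sets the weights: "the treatment group of interest will be given a weight of 1/PS, and the comparator group will be given a weight of 1/(1-PS". Protocol section 9.7 has the same rule ("the comparator group will be given a weight of 1/(1-PS"). The only control on the weights is trimming: "The most extreme 1% of PS values (IPTW with trimming) will be excluded to improve comparability between exposure groups". The hazard ratio (HR) comes from a Cox model "weighted on the estimated PS according to the IPTW approach". SAP Tables 17 to 19 report weighted HRs with 95% CIs overall, by bleeding site and by subgroup, and an interaction P-value below 0.05 is read as a significant difference.

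Neither document mentions stabilised or normalised weights, or a robust, sandwich or bootstrap variance. The one interval method named is Poisson, for incidence rates. On software the SAP says "All statistical analyses will be performed using SAS Enterprise Guide 7.1", with no procedure or covariance option. The protocol leaves detailed methods to the SAP, and the SAP lists no stand-alone documents, so no later document is named that would settle the point.

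**The concern.** Weights of 1/PS and 1/(1-PS) scale each arm up to the size of the whole cohort, so the weighted sample counts about two patients for every real one. The model-based variance of a weighted Cox fit treats that weighted total as independent information. The point estimate is not affected, but its stated precision is.

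The weighted HR with its CI is the Phase II primary result. Intervals that are too short would declare differences in bleeding between a NOAC and warfarin that the data do not support. The planned PS sensitivity analyses change the trimming, the adjustment or the weights. None varies the variance estimator, so none tests for this directly.

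**Working it through.** **Inputs.** From the study size sections (protocol 9.5, SAP 9): two-sided alpha 0.05 and 80% power; NOAC shares p = 83/211 = 0.393 (apixaban), 264/382 = 0.691 (rivaroxaban), 57/184 = 0.310 (edoxaban) and 26/155 = 0.168 (dabigatran); event probabilities 1.19%, 8.1%, 8.5% and 1.4%; projected totals 49,224, 89,124, 42,924 and 36,162.

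**1. The plan's own figure.** The documents give no standard error (SE) or CI width, so the sample size is what can be reproduced. The Schoenfeld formula is N = (1.960 + 0.842)² / [p(1-p) (ln HR)²] / P(event). For apixaban at HR 0.75: 7.849 / (0.2386 × 0.08276) = 397.4 events, and 397.4 / 0.0119 = about 33,397, against 33,340 stated. All eight stated sizes reproduce to within 1%. This formula counts each real patient once.

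**2. Size of the weighted sample.** The expected sum of 1/PS over NOAC users is N, and that of 1/(1-PS) over warfarin users is also N. The mean weight is therefore 2 at any allocation.

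**3. SE ratio at constant PS = p, under the null, with D events.**
- Real events per arm are Dp and D(1-p), so the true var(log HR) = 1/(Dp) + 1/(D(1-p)) = 1/(Dp(1-p)).
- Weighted events per arm are D and D, so the model-based var = 2/D.
- Model-based SE / true SE = sqrt(2p(1-p)). Coverage = 2Φ(1.96 × ratio) - 1.

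| Comparison | p | SE ratio | Coverage of nominal 95% CI | Type I error |
|---|---|---|---|---|
| Apixaban | 0.393 | 0.69 | 82% | 17.6% |
| Rivaroxaban | 0.691 | 0.65 | 80% | 20% |
| Edoxaban | 0.310 | 0.65 | 80% | 20% |
| Dabigatran | 0.168 | 0.53 | 70% | 30% |

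D cancels, so a larger cohort does not help. The ratio is largest at p = 0.5, where it is sqrt(0.5) = 0.71 and coverage is about 83%. No allocation share rescues the model-based interval.

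**4. What this does to one interval.** For dabigatran, D = 36,162 × 0.014 = 506. Model-based SE = sqrt(2/506) = 0.063; true SE = sqrt(1/(506 × 0.1396)) = 0.119. For an assumed observed HR of 0.85 the 95% CI is 0.75 to 0.96 with the first and 0.67 to 1.07 with the second.

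**5. PS spread.** The documents give none, so it was assumed: logit SD 0.5 and 1.0, true HR 1, one confounder, 1% trimming taken as 0.5% per tail, 150 to 400 runs per scenario. Coverage with raw weights and model-based variance, at SD 0.5 and then 1.0:
- apixaban 84%, 75%
- rivaroxaban 80%, 67%
- edoxaban 78%, 76%
- dabigatran 67%, 63%

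Monte Carlo error here is roughly 2 to 4 points. With a robust sandwich variance and the same raw weights, coverage was 93% to 97% in every scenario. With stabilised weights and model-based variance it was 94% (apixaban and dabigatran, SD 0.5) and 90% (dabigatran, SD 1.0).

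**6. Reach.** The site-specific HRs, subgroup HRs and interaction P-values use the same weights. For the standardized mortality ratio (SMR) weights, which are 1 and PS/(1-PS), weighted events at constant PS are Dp in each arm. The model-based var is 2/(Dp) and the SE ratio is sqrt(2(1-p)): 1.10 apixaban, 0.79 rivaroxaban, 1.17 edoxaban, 1.29 dabigatran. That is too narrow for rivaroxaban and too wide for the other three.

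**The case against.** The strongest reply is that the plan specifies no variance, so it cannot be said to specify a wrong one. An analyst who adds a robust option would get valid intervals and still comply with the SAP. The weighting sentence also cites two methods papers on PS weighting, whose content cannot be judged here. This stands as far as it goes: a reader might infer that the documents prescribe intervals that are too narrow, and they do not. It does not make the gap harmless. The weights, trimming rule and model are all fixed in writing, and the one missing item decides whether the interval is valid.

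Three further inferences are not supported:
- **That raw weights are themselves an error.** They are not; the simulation in step 5 shows adequate coverage with them once the variance is robust.
- **That Figure 6 misuses weighted counts.** Its title ("Number of weighted events, incidence rate, and hazard ratio of major bleeding events associated with NOAC use versus warfarin") might suggest Poisson intervals on weighted events. Its layout is not shown, and Table 17 has plain columns for events and person-years, so no error is alleged there.
- **That every planned HR is affected.** The analyses with the PS as a covariate and in deciles are unweighted and escape the problem.

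It is also true that PS spread does not worsen coverage in every case (apixaban at SD 0.5), and that Phase II is conditional on power and feasibility.

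**Conclusion.** The concern holds as a conditional one. Run with the stated weights and model and nothing added, the Phase II main analysis gives CIs 53% to 69% as wide as they should be. A nominal 5% test then rejects a true null about 18% to 30% of the time, with dabigatran the worst case.

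These figures assume that the model-based variance is kept, that the PS is constant, that there is no true effect, and that the 2018 sample shares apply to the study cohort. Other shares change the size but not the direction. PS spread can make it worse, by an amount the documents do not allow one to fix. The stated sample sizes are not in question, though they make no allowance for extra variance from PS spread. The variance should be settled before any Phase II comparison is run.

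**What to change.** In SAP section 10 and protocol section 9.7, state that every weighted HR (overall, by site, by subgroup and SMR-weighted) and every interaction test uses a robust sandwich variance, or a bootstrap that re-estimates the PS in each resample. This is the essential change and is sufficient with the plan's raw weights.

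As a useful addition, replace the raw weights with stabilised ones, p/PS and (1-p)/(1-PS). They remove most of the inflation but are not enough alone when PS spread is large.

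If Figure 6 is to show CIs for weighted rates, state the method and do not use Poisson intervals on weighted counts.

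The cost is a sentence or two in each document and one procedure option, with no new data. The main-analysis CIs become wider, which is their correct width.
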